2. LIST OF ABBREVIATIONS

Term	Definition / description
AE	Adverse Event
AR(1)	Autoregressive covariance matrix of order 1
BI	Boehringer Ingelheim
CGI-I	Clinical Global Impressions – Improvement
CGI-S	Clinical Global Impressions – Severity
C-SSRS	Columbia- Suicide Severity Rating Scale
CTP	Clinical Trial Protocol
CTR	Clinical Trial Report
CYP	Cytochrome P450
EC	Exclusion Criteria
ECG	Electrocardiogram
EOS	End of Study
EOT	End of Treatment
eCRF	Electronic Case Report Form
FAS	Full Analysis Set
FU	Follow Up
H_0	Null Hypothesis
TT	A 1, 4' TT 41 '

FAS	Full Analysis Set
FU	Follow Up
H_0	Null Hypothesis
H_a	Alternative Hypothesis
HR	Hazard Ratio
IC	Inclusion Criteria
ICD-10	International Statistical Classification of Diseases and Related Health Problems, 10 th Revision
ICF	Informed Consent Form
ICH E9	International Conference on Harmonization of Technical Requirements for Registration of Pharmaceuticals for Human use, E9-Statistical Principles for Clinical Trials
IPD	Important Protocol Deviation
ITT	Intent To Treat

Proprietary confidential information © 2021 Boehringer Ingelheim International GmbH or one or more of its affiliated companies

Term Definition / description

LTFU Lower Level Term
LTFU Lost to Follow-up

Max Maximum
Min Minimum

MINI Mini-International Neuropsychiatric Interview

MMRM Mixed Model with Repeated Measurements

N Sample Size

PANSS Positive and Negative Syndrome Scale

PGI-I Patient Global Impressions-Improvement

PK Pharmacokinetic

PSP Personal and Social Performance

PT Preferred Term

RRR Relative Risk Reduction

RS Randomized Set
SD Standard deviation
SOC System Organ Class

TOEPH Toeplitz with Heterogeneous Variances

TOEP standard Toeplitz matrix

TS Treated Set

TSAP Trial Statistical Analysis Plan

T/W Taper/Withdrawal

VAS Visual Analogue Scale

Proprietary confidential information © 2021 Boehringer Ingelheim International GmbH or one or more of its affiliated companies

3. INTRODUCTION

As per ICH E9, the purpose of this document is to provide a more technical and detailed elaboration of the principal features of the analysis described in the protocol, and to include detailed procedures for executing the statistical analysis of the primary and secondary variables and other data.

This TSAP assumes familiarity with the Clinical Trial Protocol (CTP), including Protocol Amendments. In particular, the TSAP is based on the planned analysis specification as written in CTP Section 7 "Statistical Methods and Determination of Sample Size". Therefore, TSAP readers may consult the CTP for more background information on the study, e.g., on study objectives, study design and population, treatments, definition of measurements and variables, planning of sample size, randomization.

SAS® Version 9.4 or higher will be used for all analyses.

Proprietary confidential information © 2021 Boehringer Ingelheim International GmbH or one or more of its affiliated companies

4. CHANGES IN THE PLANNED ANALYSIS OF THE STUDY

CTP section 7.5 specifies: All patients will be followed up for relapse [...]. Any patient who has not relapsed will be censored in the analysis of the primary endpoint at the time of last patient contact. In fact, the primary endpoint analysis is the ITT analysis, which is indicated in CTP section 7.3 to include relapses only during the 28-week planned on-treatment period. See Section 6.6 for corrections.

The following additional analyses, which were not mentioned in the CTP, were added:

- Time to Discontinuation was added as a further endpoint.
- Time to Treatment Discontinuation or Relapse was added as a sensitivity analysis to the primary endpoint

Recruitment to this study was stopped early by the Sponsor due to slow enrolment. As a result, statistical power is reduced because of sample size reduction, analyses remain the same as planned, see more details in Section 7.4. A fast-track approach will be taken in order to expedite decision making and for preparation of the planned phase III trials, see more details in Section 9.2.

Details surrounding the planned assessment of the impact of the COVID-19 pandemic on the trial, are specified in section 9.3.

Hazard ratio calculated from the Cox proportional hazard model and a 95% confidence interval around the HR will be provided for primary and secondary endpoint; relative risk reduction and a 95% confidence interval around the RRR will be provided for further endpoints.

Due to the fact that there were cases where the site was not able to enter the data into the iPad in a timely manner and was unable to confirm with the site the actual date the assessment was completed, visit start date as recorded on the CRF will be used as the analysis date. Confirmed that all assessments started on the visit date and therefore it is a reasonable assumption to use the CRF recorded visit date as the analysis date.

5. ENDPOINTS

The overall objective of this study is to evaluate the efficacy and safety of BI 409306 during a 28-week period in patients with schizophrenia, who are on stable background antipsychotic treatment. Refer to Sections 2 and 7 of the CTP for more details on the endpoints of the study.

5.1 PRIMARY ENDPOINT(S)

The primary endpoint will be used as defined in the revised **CTP**, **Section 2.1.2**:

The primary endpoint is time to first relapse until study end (planned at 28 weeks). Time of relapse will be obtained by selecting the earliest date from any, or all of the following 6 criteria:

- Time to hospitalization (involuntary or voluntary admission), intensive outpatient therapy or use of home treatment, as an alternative to hospitalization, for decompensation of schizophrenia symptoms
- Time to an assessment on the Clinical Global Impressions Severity (CGI-S) of ≥ 5 (markedly ill) and either:
 - an increase on any of the following individual PANSS items: conceptual disorganization, hallucinatory behavior, suspiciousness, unusual thought content to a score > 4 with an absolute increase of ≥2 on that specific item since randomisation

or

- an increase on any of the following individual PANSS items: conceptual disorganization, hallucinatory behavior, suspiciousness, unusual thought content - to a score > 4 and an absolute increase of ≥4 on the combined 4 PANSS items since randomisation

or

- PANSS total score increase of ≥25% relative to baseline score or an increase of ≥10 points if baseline score was ≤40
- Time to a prescription for a new antipsychotic or time to an increase in dose of an ongoing antipsychotic medication for significant worsening of schizophrenia symptoms
- Time to clinically significant homicidal ideation, in the investigator's judgement
- Time to suicidal behavior, or time to assessment of suicidal ideation type 4 or 5 on the Columbia Suicide Severity Rating Scale (C-SSRS)
- Time to deliberate self-injury and/or violent behaviour resulting in suicide or in clinically significant injury to the patient or another person or property damage, in the investigator's judgement

Proprietary confidential information © 2021 Boehringer Ingelheim International GmbH or one or more of its affiliated companies

5.2 SECONDARY ENDPOINT(S)

5.2.1 Key secondary endpoint

The key secondary endpoint as described in **Section 2.1.3 in the revised CTP** is:

Change from baseline in Positive and Negative Symptom Score (PANSS) positive symptoms score after 28 weeks of treatment.

See section 6.7 for details regarding the definition of "baseline".

5.2.2 Secondary endpoints

The secondary endpoints are described in **Section 2.1.3 in the revised CTP**:

- Time to new prescription or increase in dose of an ongoing antipsychotic medication.
- Change from baseline in Clinical Global Impressions –Severity (CGI-S) scale score after 28 weeks of treatment.
- Patient Global Impressions-Improvement (PGI-I) scale score after 28 weeks of treatment.
- Suicidal ideation and behaviour as assessed by C-SSRS after 28 weeks of treatment.
- Change from baseline in Personal and Social Performance scale (PSP) score after 28 weeks of treatment.

See section 6.7 for details regarding the definition of "baseline".

5.4 OTHER VARIABLES

5.4.1 Demographic and other baseline characteristics

Demographics:

- Sex
- Race
- Ethnicity
- Region (North America, Europe, Asia)
- Country (Canada, USA, France, Japan, Taiwan, South Korea)
- Age [years]
- Age in classes (18-<35; 35-<50; >=50)
- Weight (kg)
- Height (cm)
- Body Mass Index [kg/m²]: Weight [kg]/(Height[m]*Height[m]), as continuous variable and in classes (<18.5; >=18.5 to <25; >=25 to <30; >=30)
- Ethnicity
- Smoking history
- Alcohol Consumption
- Cannabis usage
- Time since diagnosis of schizophrenia [years]

- Education (self) [years]
- Education (childrearing mother) [years]
- Student (within past 6 months)
- Living arrangements
- Employment status

Other baseline characteristics:

- Baseline conditions/Medical history
- Baseline clinical assessments (CGI-S, C-SSRS, PANSS (total, conceptual disorganization, hallucinatory behavior, suspiciousness, unusual thought content positive, negative, general), PSP (total, socially useful activity, personal and social relationships, self-care, disturbing and aggressive behaviour) AIMS, EQ-5D-5L)
- Concomitant Antipsychotic Medication
- Concomitant Medication
- Concomitant Non-Drug Therapy
- Psychotherapy

Pharmacogenomic data:

• CYP2C19 (UM, EM, IM, PM, ND, Missing)

5.4.2 Treatment compliance and treatment exposure

Treatment compliance:

Treatment compliance is assessed via the use of the AICURE device and the eCRF. Average adjusted compliance will be calculated and displayed. Compliance will be categorized into classes: <80%, >=80% to <=100%, >100%.

Treatment exposure:

- Exposure is calculated as (drug stop date) (drug start date) +1
- Treatment exposure classes (<=102 days, 103 days to <=204 days, >204 days)

The Taper/Withdrawal (T/W) period is included in the treatment exposure calculation.

Study observation periods:

• Each patient's observation time contribution, for the Intent to Treat (ITT) follow-up, and Full follow-up period, will be summarized, for more details see Section 6.1.

5.4.3 Pharmacokinetic assessments

As described in **Section 5.3.1 of the CTP**:

• $C_{0:45h}$: measured plasma concentration of BI 409306 in plasma 0:45h after a single dose of BI 409306

- C_{1.5h}: measured plasma concentration of BI 409306 in plasma 1.5h after a single dose of BI 409306
- C_{2h}: measured plasma concentration of BI 409306 in plasma 2h or more after a single dose of BI 409306

From the individual pharmacokinetic parameters $C_{0:45h}$ and $C_{1.5h}$, mean pharmacokinetic parameters will be calculated by descriptive statistics if data allow.

At the post-randomisation visits, the following pharmacokinetic parameters will reported for each analyte:

• C_{press}: residual concentration of BI 409306 and metabolites CD 13896 and CD 14084 in plasma after last dose of BI 409306

Per CTP flow-chart, pharmacokinetic sampling will be performed at Visits 8 and 16.

5.4.4 Pharmacogenomic evaluation

As specified in the **Section 5.4.2 of the CTP**:

One blood sample will be taken at the screening visit for genotyping of CYP2C19 from all patients taking medication known to be strong or moderate inhibitors of CYP1A2.
[...]

In case of a positive study outcome, the sample may be used for DNA extraction and subsequent genotyping for variants in genes involved in absorption, distribution, metabolism and elimination of the compound. It is not intended to include these data in the final report. However, the data may be part of the report if necessary.

In case of a positive study outcome as determined based on topline results, samples from all subjects will be genotyped for CYP2C19. The influence of CYP2C19 variations on pharmacokinetics will be explored descriptively and if applicable by population pharmacokinetic methods. The parameters $C_{0.45h}$ and $C_{I.5h}$ of BI 409306 in plasma will be compared in exploratory figures by CYP2C19 diplotype and predicted phenotype, if applicable; these analyses will be presented in section 15.6 of the CTR.

TSAP for BI Trial No: 1289-0049 Page 14 of 35

Proprietary confidential information © 2021 Boehringer Ingelheim International GmbH or one or more of its affiliated companies

6. GENERAL ANALYSIS DEFINITIONS

6.1 TREATMENT(S)

As described in Section 3 of the revised CTP, patients will be randomized in equal allocation to one of three treatment dosage groups (50 mg, 25 mg and placebo) for analysis purposes.

For randomization purposes 6 arms have been defined:

- BI 409306 50 mg q.d for 28 weeks and 7 days of withdrawal from treatment
- BI 409306 50 mg q.d for 28 weeks and 7 days of tapering from treatment
- BI 409306 25 mg q.d for 28 weeks and 7 days of withdrawal from treatment
- BI 409306 25 mg q.d for 28 weeks and 7 days of tapering from treatment
- Placebo for 28 weeks and 7 days of withdrawal from treatment
- Placebo for 28 weeks and 7 days of tapering from treatment

Table 6.1: 1 Treatments and their labels per randomization list

Treatment	Short label
BI 409306 50 mg q.d. taper	BI 409306 50 mg taper
BI 409306 50 mg q.d. withdraw	BI 409306 50 mg withdraw
BI 409306 25 mg q.d. taper	BI 409306 25 mg taper
BI 409306 25 mg q.d. withdraw	BI 409306 25 mg withdraw
Placebo taper	Placebo taper
Placebo withdraw	Placebo withdraw

The treatment period is defined as 28 weeks, hence for most analyses the taper/withdrawal period will not be considered and the arms corresponding to the same doses of treatment will be pooled, resulting in the following treatment labels for displays.

Table 6.1: 2 Treatments and their labels in specified analyses

Treatment (per rand list)	Short label (in displays)	
BI 409306 50 mg q.d. taper	DI 400206 50 mg	
BI 409306 50 mg q.d. withdraw	BI 409306 50 mg	
BI 409306 25 mg q.d. taper	DI 400206 25 ~	
BI 409306 25 mg q.d. withdraw	BI 409306 25 mg	

Proprietary confidential information © 2021 Boehringer Ingelheim International GmbH or one or more of its affiliated companies

Treatment (per rand list)	Short label (in displays)
Placebo taper	Placebo
Placebo withdraw	Piacedo

The trial consists of a 28 day screening period, followed by a 28 week treatment period (after randomization), followed by a 7 day taper/withdraw (T/W) period and a 21day follow-up.

For analysis purposes three periods have been defined in section 7.3.1 of the CTP:

• Intent to Treat (ITT) follow-up

This is the intended 28 week treatment period. It does not include the T/W period. For patients who discontinue early, their follow-up information until the end of the planned 28 week treatment period is included.

• Full follow-up

This is the entire study period, beginning with randomization until the end of the follow-up period (or date of last contact), including the T/W period and follow-up period. (Sensitivity for ITT follow-up analysis)

• On-treatment

This includes the time period from treatment start date until drug discontinuation + 7 days.

- Patients randomized to withdrawal period/early discontinued patients:
 Time on treatment prior to withdrawal (or early discontinuation) + 7 days
- Patients randomized to taper period:
 Time on treatment + 7 days taper period + 7 days

Patients who discontinue early will be followed up according to the CTP.

6.2 IMPORTANT PROTOCOL DEVIATIONS

Handling of iPDs in analysis is included in the DV domain specifications and stored within the Trial Master File (TMF) in the electronic Document Management System (eDMS).

6.3 SUBJECT SETS ANALYZED

Screened Set

The screened set includes all patients who were screened for the trial, gave informed consent and had at least one screening procedure at Visit 1.

Randomized Set (RS)

The RS consists of all patients who were screened for the trial and who were randomized to study drug, regardless of whether any study drug was taken.

Treated Set (TS)

The TS includes all patients who were randomized and were documented to have taken at least one dose of study drug.

Full Analysis Set (FAS)

The FAS includes all patients in the TS with at least one baseline and post-baseline measurement of any type. The FAS will be used for the primary and secondary analyses. The screened set, and treated set will be used to populate patient disposition and the TS will be used for demographics, baseline characteristics, treatment exposure and safety analyses (including adverse events, laboratory measurements, and vital signs). Safety analyses will assign patients to the treatment group based on the treatment they received at the time the AE occurred.

Efficacy data will always be analyzed according to the randomized treatment following the intention-to-treat (ITT) principle. If a patient erroneously received a medication kit that included a treatment different from what they were randomized to, the patient's efficacy data will be analyzed according to the treatment they were originally randomized to.

Table 6.3: 1 Subject sets analyzed

		Subject set
Class of endpoint	TS	FAS
Primary and key secondary endpoints		X
(other) Secondary and further endpoints		X
Safety endpoints	X	
Demographic/baseline endpoints	X	

Analysis periods are defined in the revised CTP and in Section 6.1.

6.5 POOLING OF CENTRES

The randomization was stratified by country.

6.6 HANDLING OF MISSING DATA AND OUTLIERS

Assessment of relapse data (primary endpoint):

All patients will be followed up for relapse [...]. Any patient who has not relapsed will be censored in the analysis of the primary endpoint at the time of their planned complete 28-week treatment period. This does not include the T/W period. For AEs that meet the primary endpoint criteria, missing or incomplete AE dates are imputed according to BI standards.

The sensitivity analysis will use the Full Follow-up period to demonstrate the robustness of the results of the main analysis. See revised CTP Section 7.3

PANSS positive symptoms (key secondary analysis)

Change from baseline in PANSS positive symptoms will be evaluated using Mixed effect Model for Repeated Measures (MMRM) approach. This approach allows for missing data, assuming they are missing at random. All patients can be included in the model and missed visits will not be imputed. If a PANSS item is missing, the missing score on that individual PANSS item will not be imputed; if individual PANSS item is missing within a PANSS subscale, this subscale cannot be included in the calculation of the overall PANSS total score. Therefore, patients with missing individual PANSS items will also have a missing PANSS total score at that visit. However, subscale scores will be used for analysis if none of the individual items are missing.

Relative Risk Reduction (RRR)

Per revised CTP Section 7.5.:

All patients in the FAS will be included [...] *regardless of drop-out.*

For

AE dates

Missing or incomplete AE dates are imputed according to BI standards (see "Handling of missing and incomplete AE dates") (3).

PK data

Missing data and outliers of PK data are handled according to Reference (2) and as described in Section 10 of the revised CTP.

In December 2019, during the conduct of the trial, a Visit 8 eCRF page was added to capture
the date and time of the last dose of BI drug intake before the PK sampling performed at Visit
8. For patients who had completed the trial at that time, or patients for whom the visit 8 date
had passed, the data will be used to inform the date and time of the last BI drug
intake.
Sensitivity analysis: the date and time of the last dose of BI drug intake at Visit 8 collected in
the eCRF will be compared to the information recorded in This will be done for

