### 7.3.1 Primary endpoint analyses

The primary endpoint is the time to first relapse as defined in [Section 2.1.2](#) over the ITT follow-up period (see definition in [Section 7.3](#)).

The treatment comparison strategy is specified in [Section 7.2](#). The treatment arms will be pooled according to dose, i.e. no distinction will be made between treatment arm randomised to taper or treatment arm randomised to withdrawal.

The equality of the hazard rates will be tested by the Wald test for the treatment effect in a stratified Cox proportional hazards model at the two-sided 5% significance level. The model includes the treatment effect as the only covariate and is stratified by country. Breslow's method for handling ties will be used.

The same stratified Cox proportional hazards model will be used to estimate the hazard ratio of BI 409306 vs. placebo and the asymptotic 95% Wald confidence interval. A hazard ratio of less than one favors BI 409306. The analysis will be implemented using SAS® PROC PHREG. Cox proportional hazard model assumptions will be verified.

In early discontinued patients, if the occurrence of a relapse cannot be determined between the time of discontinuation and last contact, it is assumed that no relapse has occurred. Patients who discontinue study medication will be followed until the end of the trial for the primary endpoint. Patients who are lost-to-follow up will be censored for the primary endpoint at the date of last known patient contact.

A sensitivity analysis will be conducted on the primary endpoint, using the Full Follow-up period (see definition above).

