### 7.5 HANDLING OF MISSING DATA

All patients will be followed up for relapse to the greatest possible extent as described in [Section 3.3.4.1](#). Any patient who has not relapsed will be censored in the analysis of the primary endpoint at the time of last patient contact. For any secondary analysis using RRR, all patients in the FAS will be included in the calculation of the RRR, regardless of dropout.

For the key secondary analyses, if a patient misses a visit, the data will not be imputed. The mixed effects model will handle missing data based on a likelihood method under the “missing at random” assumption.

Further details about handling missing data will be specified in the TSAP.

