7.4.1 Primary efficacy analysis

The primary analysis will be conducted on the FAS using the ITT follow-up period as defined in Section 6.1. Because the ITT covers the 28 weeks of planned treatment and not the T/W period, the treatment arms will be pooled according to dose and disregarding the T/W randomization.

Revised CTP in Section 7.3.1:

The equality of the hazard rates will be tested by the Wald test for the treatment effect in a stratified Cox proportional hazards model at the two-sided 5% significance level. The model includes the treatment effect as the only covariate and is stratified by country. Breslow's method for handling ties will be used.

The same stratified Cox proportional hazards model will be used to estimate the hazard ratio of BI 409306 vs. placebo and the asymptotic 95% Wald confidence interval. A hazard ratio of less than one favors BI 409306. The analysis will be implemented using SAS® PROC PHREG. Cox proportional hazard model assumptions will be verified.

In early discontinued patients, if the occurance of a relapse cannot be determined between the time of discontinuation and last contact, it is assumed that no relapse has occurred. Patients who discontinue study medication will be followed until the end of the trial for the primary endpoint. Patients who are lost-to-follow up will be censored for the primary endpoint at the date of last known patient contact.

According to the CTP, we have specified more details regarding efficacy analysis using ITT FU and Full FU:

Definition of last at-risk date:

The last at-risk date determined as the latest date among: the date of first dose of study medication, the date of last drug administration, all the visit start dates (including phone contact dates in which the patient was reached and follow-up contact dates) and start or stop dates of events reported on the adverse event forms.

If a patient dies, the date of death is their last at-risk date.

Definition of Visit 16 date:

The date of Visit 16 for the determination of the ITT FU period end date will be the start date recorded on eCRF.

Time to event calculations:

A. Patients completing treatment period and study period (for ITT analysis):

Events (relapses) are counted in the ITT time to event analysis whenever they occur between the first dose of randomized treatment and the patient's Visit 16 date or the date of last dose if this occurred after visit 16. (In SDTM this is EPOCH=TREATMENT1)

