- Patients with event counted: <date of event> <date of first drug administration> +1 day
- Patients without event counted: <date of last dose of study drug or date of Visit 16> <date of first drug administration >+1 day
- B. Patients completing treatment period and study period (for Full FU analysis): Events (relapses) are counted in the FU time to event analysis whenever they occur between the first dose of randomized treatment and the patient's EOS date.
 - Patients with event counted: <date of event> <date of first drug administration> +1 day

- Patients without event counted: <date of EOS> <date of first drug administration
- C. Patients who chose Early Discontinuation Option 1 or Option 2 per CTP (ITT and Full FU analysis):
- And completed required study period: Events (relapses) are counted in the time to event analysis whenever they occur between the first dose of randomized treatment and the patient's EOS date.
 - Patients with event counted: <date of event> <date of first drug administration> +1
 - Patients without event counted: <date of EOS> <date of first drug administration >+1 day
- And discontinued or did not complete required study period: Events (relapses) are counted in the time to event analysis whenever they occur between the first dose of randomized treatment and the patient's last at-risk date.
 - Patients with event counted: <date of event> <date of first drug administration> +1 day
 - Patients without event counted: <date of last at-risk date > <date of first drug administration >+1 day
- Patients who chose Early Discontinuation Option 3 or Option 4 per CTP (ITT and D. Full FU analysis):
- And completed required study period: Events (relapses) are counted in the time to event analysis whenever they occur between the first dose of randomized treatment and the patient's End of Study Date.
 - Patients with event counted: <date of event> <date of first drug administration> +1
 - Patients without event counted: < date of EOS > < date of first drug administration >+1 day
- And discontinued or did not complete required study period: Events (relapses) are counted in the time to event analysis whenever they occur between the first dose of randomized treatment and the date of last at-risk date.
 - Patients with event counted: <date of event> <date of first drug administration> +1
 - Patients without event counted: < date of last at-risk date > < date of first drug administration >+1 day

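### SAP 6.6 words the primary-endpoint censoring of non-relapsers as a fixed 28-week date, not an upper limit, which conflicts with the earlier dates in SAP 7.4.1

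*SAP*

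**What the plan says.** **The protocol.** Protocol 7.5 states: "Any patient who has not relapsed will be censored in the analysis of the primary endpoint at the time of last patient contact". Protocol 7.3.1 says of lost patients: "Patients who are lost-to-follow up will be censored for the primary endpoint at the date of last known patient contact".

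**The SAP's correction.** SAP 4 objects to Protocol 7.5 because the primary analysis is the ITT analysis, "which is indicated in CTP section 7.3 to include relapses only during the 28-week planned on-treatment period", and points to SAP 6.6 for the corrected rule. SAP 6.6 then says that any non-relapser "will be censored in the analysis of the primary endpoint at the time of their planned complete 28-week treatment period", excluding the taper/withdrawal (T/W) period. It makes no exception for patients no longer under observation and has no wording for whichever date comes first.

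**The SAP's detailed rule.** SAP 7.4.1 concerns the same analysis: "The primary analysis will be conducted on the FAS using the ITT follow-up period as defined in" SAP 6.1. It repeats the protocol's lost-to-follow-up sentence and then gives end dates by patient category:
- Completers (category A): Visit 16, or the last dose if later, with the note "In SDTM this is EPOCH=TREATMENT1".
- Early discontinuers under Options 1 to 4 (categories C and D) who complete the required period: end of study (EOS).
- Options 1 to 4, not completing: last at-risk date. For category D, relapses count "whenever they occur between the first dose of randomized treatment and the date of last at-risk date".
- Consent withdrawn: date of withdrawal.
- Lost to follow-up: last at-risk date.
- Deaths have no category of their own and enter through a definition: "If a patient dies, the date of death is their last at-risk date".

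**The concern.** A non-relapser lost at, say, week 10 has two censoring dates for the primary endpoint in one SAP: week 10 under 7.4.1 and week 28 under 6.6. No sentence says which section prevails. SAP 6.6 cannot be dismissed as stray text, because SAP 4 lists it as a deliberate correction.

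If 6.6 were programmed as written, patients who can no longer be seen to relapse would stay in the risk set as relapse-free until week 28, including after a death not preceded by relapse. Unequal loss between arms would then distort the hazard ratio.

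The two sections are also incomplete in opposite ways. SAP 6.6 gives the 28-week limit without the earlier end of observation. SAP 7.4.1 gives the earlier end, but its formulas for categories C and D are labelled for both the ITT and full follow-up analyses and run to EOS without repeating the limit, which comes in only by reference to SAP 6.1. This can matter: under Protocol 6.2.2, an Option 1 patient who stops drug less than 4 weeks before Visit 16 has a follow-up visit 28 days after the EOT visit, which can fall after week 28.

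**Working it through.** **1. The plan's own figures.** Protocol 7.7 assumes 30% placebo relapse, HR 0.50, two-sided alpha 0.05, 80% power, 20% dropout and 1:2 allocation.
- Events = (1.960 + 0.842)² / [(1/3)(2/3)(ln 0.5)²] = 7.849 / 0.1068 = 73.5, so 74, as stated.
- With exponential relapse and dropout, the event probability is 0.271 on placebo and 0.147 on active, mean (0.271 + 2 × 0.147)/3 = 0.188. Then N = 73.5/0.188, about 391, against the plan's 385 (1.5% off).

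The censoring conflict does not alter these figures.

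**2. Dates side by side, non-relapser leaving before week 28**

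| Patient | SAP 7.4.1 | SAP 6.6, literal |
|---|---|---|
| Lost to follow-up | last at-risk date | week 28 |
| Options 1-4, not completing | last at-risk date | week 28 |
| Consent withdrawn | withdrawal date | week 28 |
| Died without relapse | date of death | week 28 |
| Discontinued drug, followed to week 28 | about week 28 | week 28 |

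Only unobserved patients are affected.

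**3. Kaplan-Meier estimate under literal 6.6.** Take exponential relapse (rate λ) and independent exponential loss (rate μ), with time in units of 28 weeks. Under literal 6.6 every non-event stays at risk to week 28, so the Kaplan-Meier estimate equals the crude proportion:

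λ/(λ+μ) × [1 − exp(−(λ+μ))]

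- True 30%, loss 10%: λ = −ln 0.7 = 0.357, μ = −ln 0.9 = 0.105. Result 0.772 × 0.370 = 28.6%.
- True 30%, loss 20%: μ = 0.223. Result 0.615 × 0.440 = 27.1%.

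The crude proportion is the same under 7.4.1, because the same events are counted. What differs is that Kaplan-Meier under 7.4.1 recovers 30% when loss is independent.

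Patients affected at 10% loss: μ/(λ+μ) × 0.370 = 0.228 × 0.370 = 8.4%, or about 33 of 387. Each is credited on average with 28 × [1 − (1/0.462 − 0.630/0.370)] = 28 × 0.538 = 15.1 unobserved weeks.

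**4. Hazard ratio and false superiority.** Simulated trials: true HR 1, N=387, 1:2 allocation, 30% relapse, Cox model with Breslow ties, superiority at two-sided 5% (nominal 2.5% in the favourable direction), 40,000 trials per row (Monte Carlo SE about 0.1 point). Loss by arm is **assumed**; the documents give only 20% dropout overall. Average loss is (placebo + 2 × active)/3.

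| Loss placebo/active | Average | HR 7.4.1 | HR 6.6 | False superiority 7.4.1 | 6.6 |
|---|---|---|---|---|---|
| 10/10% | 10% | 1.003 | 1.004 | 2.7% | 2.7% |
| 7.5/12.5% | 10.8% | 1.005 | 0.977 | 2.7% | 3.6% |
| 5/12.5% | 10% | 1.003 | 0.961 | 2.8% | 4.4% |
| 12.5/7.5% | 9.2% | 1.003 | 1.033 | 2.7% | 2.0% |
| *Outer bound* 10/25% | 20% | 1.003 | 0.915 | 2.8% | 7.0% |
| *Outer bound* 15/25% | 21.7% | 1.005 | 0.944 | 2.6% | 5.1% |

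The last two rows use up or exceed the plan's whole 20% dropout, as if no discontinuer were followed, so they are limits and not expectations. For 5/12.5%, a separate 12,000-trial run gave 4.0% and a 4,000-trial run 3.7% (SE 0.3), so 4.0 to 4.4% is a fair range. Six country strata with assumed sizes and relapse rates gave 3.5% (7.5/12.5%) and 4.4% (5/12.5%).

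**5. Smaller trial.** SAP 4 reports that recruitment stopped early; final N is not given. At assumed N of 258, 195 and 129, the two middle patterns give 3.5 and 3.8%, 3.2 and 3.8%, and 3.2 and 3.3% under literal 6.6. The HR ratio of 6.6 to 7.4.1 stays at 0.972 and 0.958; only the precision falls.

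**6. If the drug works.** At true HR 0.5 and N=387, power under 7.4.1 and 6.6 is 85.1 and 84.7% (10/10%), 85.1 and 87.3% (7.5/12.5%), and 85.1 and 82.0% (12.5/7.5%).

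**The case against.** The strongest reply is that the plan largely settles this itself. SAP 7.4.1 presents itself as the more detailed specification for the ITT and full follow-up analyses and gives a formula for each category. SAP 4 corrects only Protocol 7.5, for the stated purpose of limiting relapses to 28 weeks, and declares no change to the lost-to-follow-up rule of Protocol 7.3.1, which 7.4.1 reproduces. A programmer following 6.6 literally would have to override all of that. This stands: 6.6 was very probably meant as a cap, and with 7.4.1 followed it has no effect. It does not remove the defect, because the sentence is still wrong as written and the two rules are not ranked.

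Three further limits stand.
- Options 1 to 4 exist to keep discontinuers under relapse follow-up, so dropout is not the same as loss.
- Suicide is itself a relapse criterion, so the point about time after death concerns only other deaths without prior relapse.
- SAP 7.4.1 is not bias-free in general. The figures above assume independent loss, and both documents presume no relapse where it cannot be determined between discontinuation and last contact. That presumption stops at last contact and so does not support relapse-free credit beyond it.

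**Conclusion.** Wrong as written; minor to should-fix. The textual conflict is certain. Its effect is conditional on two things together: literal programming of 6.6 against 7.4.1, and unobserved loss that differs between arms. Under both, with the assumed 7.5/12.5% and 5/12.5% patterns at N=387, a true HR of 1 reads about 0.98 and 0.96, with false superiority of about 3.6% and 4.0 to 4.4%. The excess is smaller at the reduced N. More loss on placebo biases against the drug.

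A reader might infer more than the documents support:
- *That the primary analysis will be biased towards the drug.* It need not be: 7.4.1 very probably governs, no loss by arm is given, and the direction depends on which arm loses more patients.
- *That relapse proportions would be understated.* Events and events/N are identical under both rules. Only the Kaplan-Meier estimates and the risk sets change.

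**What to change.** Reword SAP 6.6 along these lines: *A patient who has not relapsed is censored at the earlier of (a) the end of the ITT follow-up period as defined in 6.1 and 7.4.1 (Visit 16, or the last dose of the 28-week treatment period if later; the planned 28-week date if there is no Visit 16; excluding the T/W period) and (b) the date given in 7.4.1 for the patient's category (EOS, last at-risk date including date of death, or consent-withdrawal date).*

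Add that 7.4.1 governs patient-level dates, and that limit (a) also applies to categories C and D in the ITT analysis, for both events and censoring.

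Cost: one or two SAP sentences and a check of the derivation code before database lock. No new data are needed, and the planned N, events and power do not change.
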